3.10. Assessment of Pharmacodynamics

Assessment of lipids/lipoproteins as discussed in Section 3.9 will cover pharmacodynamics.

4. ADVERSE EVENTS

This section will describe how the adverse events will be collected per protocol; analysis methods will be described in [Section 6.4.8.1](#).

4.1. Adverse Event

Any untoward medical occurrence in a patient or clinical trial subject administered a medicinal product and which does not necessarily have a causal relationship with this treatment. An adverse event can therefore be any unfavorable and unintended sign (eg, an abnormal laboratory finding), symptom, or disease temporally associated with the use of a medicinal product, whether or not considered related to the medicinal product.

4.2. AE Severity

The severity of AEs will be assessed by the Investigator using the 3-point scale below:

- 1 = Mild: Discomfort noticed, but no disruption to daily activity.
- 2 = Moderate: Discomfort sufficient to reduce or affect normal daily activity.
- 3 = Severe: Inability to work or perform normal daily activity.

4.3. Study Drug Causality

The relationship between the AE and the investigational product will be assessed by using a binary assessment. The investigator should determine whether there is a 'Reasonable possibility' or 'No reasonable possibility' that the investigational product caused the event based on the definitions below.

Reasonable possibility - There is a reasonable possibility that the administration of the investigational product caused the AE. There is evidence to suggest a causal relationship between the investigational product and the AE.

No reasonable possibility - There is no reasonable possibility that the administration of the investigational product caused the AE. There is no temporal relationship between the investigational product and event onset, or an alternative etiology has been established.

4.4. Serious Adverse Event

Any untoward medical occurrence that at any dose:

- Results in death,
- Is life-threatening, i.e., the subject was, in the opinion of the investigator, at immediate risk of death from the event as it occurred (it does not include an event that, had it occurred in a more severe form, might have caused death),
- Results in a significant, persistent or permanent change, impairment, damage or disruption in the subject's body function/structure, physical activities and/or quality of life,
- Requires in-subject hospitalization or prolongs hospitalization,

- Is a congenital anomaly/birth defect, or
- Is another medically significant event where medical and scientific judgement should be exercised in deciding whether other situations should be considered serious reactions, such as important medical events that might not be immediately life threatening or result in death or hospitalization but might jeopardize the patient or might require intervention to prevent one of the other outcomes listed above. Examples of such events are intensive treatment in an emergency room or at home for allergic bronchospasm, blood dyscrasias or convulsions that do not result in hospitalization or development of dependency or abuse. Any suspected transmission via a medicinal product of an infectious agent is also considered a serious adverse reaction.

A distinction should be drawn between serious and severe AEs. Severity is an estimate or measure of the intensity of an AE, while the criteria for serious AEs are indications of adverse subject outcomes for regulatory reporting purposes. A severe AE need not necessarily be considered serious and a serious AE need not be considered severe. For example, nausea that persists for several hours may be considered severe nausea, but not an SAE. On the other hand, a myocardial infarction (MI) that may be considered minor could be an SAE if it prolonged hospitalization.

4.5. Additional collection of safety data: Special Situations

4.5.1. Special Situations

Special Situations designated for this study were collected as adverse events and include:

- Medication errors that fall into the following categories
 - wrong investigational product
 - wrong dose (including overdose, underdose, change in dosing regimen, strength, form concentration, amount)
 - wrong route of administration
 - wrong subject (i.e., not administered to the intended subject)
 - accidental exposure
- Pregnancy/lactation exposures with or without any AEs related to the parent or child
- Suspected transmission via a medicinal product of an infectious agent
- Drug interactions

4.5.2. Other safety related information

Injection site reactions (ISR) including individual signs or symptoms at the injection site following investigational product administration should be recorded on specifically designed electronic case report form (eCRF) pages. Photographs of ISR, if they were obtained during the study visits, should be forwarded to the study inbox.

Other safety related information that should be reported as adverse events in accordance with the process described in Protocol Section 8.4 are:

- Abnormal neurological examination, e.g., peripheral sensory and motor evaluation, an assessment of gait, pain, position, strength and reflexes (Protocol Appendix C).
- Potential anaphylactic reactions assessed by Sampson criteria (Protocol Appendix D). If Sampson criteria are positive, confirm by elevation of tryptase in blood plasma measured within 30 minutes of symptoms.
- Hyperglycemia-related AEs:

Report 'New onset of diabetes' in subjects with no medical history of diabetes when:

- HbA1c becomes $\geq 6.5\%$ and/or
- Two consecutive values of fasting plasma glucose that are ≥ 126 mg/dL
- If a new concomitant medication for control of plasma glucose is added, further information to assess for a diagnosis of new onset diabetes will be collected.

Report 'Worsening of the glycemic control' or 'diabetic complications' in subjects with a medical history of disease (HbA1c $\geq 6.5\%$ at baseline) when:

- HbA1c increases from baseline $> 0.5\%$ and/or
- New concomitant medication or increase in dose of current antidiabetic therapy is initiated to improve the control of plasma glucose level.

5. MEASURES TO MINIMIZE/AVOID BIAS

5.1.1. Blinded Study

This study will employ a double-blind technique with a placebo control. Randomization via automated interactive response technology (IRT) will be used to assign a subject to blinded investigational product. In addition, investigational product will be dispensed and administered in a blinded syringe. Blinding will minimize bias based on subject selection, baseline characteristics, clinical endpoint and AE reporting.

6. STATISTICAL PLAN

6.1. Sample Size

The sample size calculation is performed with the assumption (which is based on the observed results from a Phase II study) that the difference in change from baseline between the active dose group and the placebo group for LDL-C will be no less than 30 mg/dL, with a standard deviation of 20 mg/dL.

Assuming about a 5% drop out rate, the sample size will be approximately 1425 subjects that are evaluable for efficacy across the placebo and inclisiran dose groups. This sample size of at least 1425 evaluable subjects, will provide more than 90% power to detect a 30% reduction of LDL-C levels in the inclisiran group compared to the placebo group at one-sided significance level of 0.025. This sample size will also contribute additional sufficient safety data.

6.2. Randomization

Subjects will be screened and approximately 1500 eligible subjects will be randomized by the IRT system: 750 subjects will be randomized to inclisiran sodium 300 mg and 750 subjects to placebo. Treatment allocation will be stratified by country and by current use of statins or other lipid-modifying therapies. Each subject will receive four SC injections of blinded inclisiran or placebo on Day 1, Day 90, Day 270, and Day 450.

6.3. General Statistical Considerations and Definitions

6.3.1. General Statistical Methods

All study-collected data will be summarized by treatment group using descriptive statistics, graphs, and/or raw data listings. Categorical variables will be summarized using counts and percentages. Percentages are based on the number of subjects in the analysis set for whom there are non-missing data, unless otherwise specified. Continuous variables, including changes from Day 1, will be summarized using descriptive statistics (n, mean, standard deviation [SD], median and interquartile range [first and third quartiles], minimum and maximum).

All p-values will be two-sided. All p-values will be rounded to three decimal places using the following algorithm. If the fourth digit of the p-value is less than or equal to 4, the p-value will be rounded down. If the fourth digit of the p-value is greater than or equal to 5, the p-value will be rounded up. All p-values rounded to 0.000 will be presented as '<0.001' and p-values that round to 1.000 will be presented as '1.000'.

Absolute change and percent change from baseline will be calculated as follows:

- Absolute Change = Value at Day X – Baseline value.
- Percent Change = (Absolute Change/Baseline value)*100%.

6.3.2. Analysis Populations

The following populations will be used for data analyses and/or presentation.

6.3.2.1. Intent-to-Treat (ITT) Population

All subjects randomized into the study will comprise the intent-to-treat (ITT) population. Treatment classification will be based on the randomized treatment. The ITT population will be used for analysis of the primary and secondary endpoints.

6.3.2.2. Full Analysis Set (FAS)

All subjects who are randomized into the study, take any study medication and have at least one post treatment lipid data measured will comprise the full analysis set (FAS) population. Treatment classification will be based on the randomized treatment.

6.3.2.3. Modified Intent-to-Treat (mITT) Population

All randomized subjects who receive at least one dose of investigational product and have both the baseline and the Day 510 follow-up LDL-C assessment will comprise the modified intent-to-treat (mITT) population. Treatment classification will be based on the randomized treatment.

6.3.2.4. Safety Population

All subjects who received at least one dose of investigational product will comprise the safety population. Treatment classification will be based on the actual treatment received. A subject who receives any amount of inclisiran throughout the study will be analyzed within the inclisiran treatment group for the safety analyses. This will be primary population for the safety analyses.

6.3.3. Analysis Windows and Baseline

The analysis windows around each visit day are provided in [Table 2](#) below.

Table 2: Analysis Windows for Each Scheduled Visit

Scheduled Visit	Analysis Window	
	From	To
Baseline		Before randomization/First Study Treatment
Day 30	Day 1	Day 60
Day 90	Day 61	Day 120
Day 150	Day 121	Day 210
Day 270	Day 211	Day 300
Day 330	Day 301	Day 390
Day 450	Day 391	Day 480
Day 510	Day 481	Day 525
Day 540	Day 526	No upper limit

Data collected at scheduled or unscheduled visits will be used in the analysis if they fall into an analysis window for a scheduled visit. If more than one visit (scheduled or unscheduled) is made

within the window specified above for any scheduled visit, the non-missing assessment closest to the scheduled visit day will be used in the analysis for that visit. However, all data will be included in the subject data listings.

Unless otherwise specified, data collected from assessments that occur more than once prior to initiation of investigational product administration, the latest assessment will be considered the "Baseline" evaluation for analysis.

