ADA=anti-drug antibodies; AE=adverse event; ECG=electrocardiogram; EOS=end of study; SAE=serious adverse event; V=visit

1. For subjects who decided to prematurely and permanently discontinue from study treatment and who decline further follow-up visits, EOS visit will be scheduled as soon as possible. If decision to discontinue is made at a specific visit, this visit will become the EOS visit and EOS visit procedures should be followed.
2. Assessment of laboratory eligibility criteria will be based on central laboratory values obtained within timeframes defined in the inclusion and exclusion criteria.
3. Only in women of childbearing potential (performed locally, prior to any dosing, using central laboratory kit supplies; urine pregnancy test)
4. Subjects will be observed in the clinic for at least 4 hours following the first injection only (Randomization visit) and 30 minutes for each subsequent visit in order to have additional vital and/or laboratory assessments completed if needed.
5. For any suspected episode of anaphylaxis, the investigator will need to collect a blood sample for tryptase within 30 minutes of an onset of anaphylaxis (or as soon as logically possible).
6. Height will be measured at baseline only and used to calculate body mass index.
7. On Day 1 vital signs will be measured prior to injection and 4 hours post injection; all other visits, vital signs are measured only prior to injection. When available, an automated BP device is recommended for collection of blood pressure (BP) and the result recorded to the nearest mmHg. The subject should be sitting at rest for at least 5 minutes prior to these assessments. One assessment for each vital sign (heart rate (HR), BP) is required per applicable visit.
8. See [Section 3.9](#) for details of specific tests to be analyzed.
9. ADA serum samples will be collected on Day 1 prior to injection and 4 hours after injection. At all other visits, ADA serum samples will be collected prior to injection only if an injection is scheduled for that visit. As presented in [Section 6](#), serum samples for analysis are collected at every visit but assessment of ADA will only occur for samples collected at the following visits: Randomization (prior to injection), Day 30, Day 150, Day 330, and Day 510. Samples will be stored for assessment (if needed) for samples collected at the following visits: Randomization (after injection), Day 90, Day 270, Day 450, End of Study Visit.

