3.3. Day 30 Visit

Subjects will return to the clinic for a follow-up visit 30 days following the first dose of investigational product. The following assessment will be completed during this visit:

- Assessment of ADA ([Section 3.8.8.7](#))
- Concomitant medications
- AE/SAE reporting

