6.4.8.5. Vital Signs

Observed value, change, and percent change from Day 1 in vital signs will be summarized descriptively at each scheduled time point by treatment group.

The change from baseline to EOS will also be summarized by the following categories:

- Systolic blood pressure (mmHg):
 - ≤ -20
 - > -20 to ≤ -10
 - > -10 to ≤ -5
 - > -5 to < 5
 - ≥ 5 to < 10
 - ≥ 10 to < 20
 - ≥ 20
- Diastolic blood pressure (mmHg):
 - ≤ -10
 - > -10 to ≤ -5
 - > -5 to ≤ -3
 - > -3 to < 3
 - ≥ 3 to < 5
 - ≥ 5 to < 10
 - ≥ 10

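### SAP Table 2 starts the Day 30 window on Day 1, so as written it labels the 4-hour post-injection vital signs as Day 30, in conflict with SAP 6.4.8.5

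*SAP*

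**What the plan says.** **Windows (SAP 6.3.3, Table 2).** The Baseline row ends "Before randomization/First Study Treatment". The next row reads "Day 30 Day 1 Day 60", meaning a Day 30 window from Day 1 to Day 60. There is no Day 1 post-dose row, and vital signs are not exempted. The rule for using the windows is general: "Data collected at scheduled or unscheduled visits will be used in the analysis if they fall into an analysis window for a scheduled visit". Where several readings share a window, "the non-missing assessment closest to the scheduled visit day will be used in the analysis for that visit". Where there are several readings before first dosing, "the latest assessment will be considered the 'Baseline' evaluation for analysis".

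**When vital signs are taken.** SAP Table 1, footnote 7: "On Day 1 vital signs will be measured prior to injection and 4 hours post injection". The same footnote limits vital signs at every other visit to the time before injection. Table 1 marks them at Screening and Days 1, 90, 270, 450 and 540, and the Day 30 cell is empty. SAP 3.3 introduces its Day 30 list with "The following assessment will be completed during this visit" and then names antibody assessment, concomitant medications and adverse events only. Protocol Table 2 and protocol sections 6.4 and 6.5 agree.

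**How vital signs are summarised (SAP 6.4.8.5).** Observed value, change and percent change from Day 1 "will be summarized descriptively at each scheduled time point by treatment group". No 4-hour time point is named.

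**The concern.** The 4-hour reading comes after first treatment, so it cannot be Baseline. It falls on Day 1, so it lies inside the Day 30 window. Nothing routine competes with it there. A programmer who applies Table 2 to vital signs would produce a Day 30 row made up almost wholly of 4-hour readings, at a visit where vital signs are not taken.

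An acute change in blood pressure or heart rate after the first injection would then appear as a one-month change. A reader looking for the post-dose result would not find it under its own label. Vital signs are one of the two reasons given in SAP 2.1 for keeping subjects in clinic for at least 4 hours after the first dose, so this is a comparison the study report should show plainly.

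**Working it through.** The plan gives no figure of its own on this point. The check applies the Table 2 windows and the closest-day rule to each scheduled vital-sign time.

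**Inputs.** Windows from SAP Table 2: Baseline before first treatment; Day 30 = Days 1–60; Day 90 = Days 61–120; Day 270 = Days 211–300; Day 450 = Days 391–480; Day 540 = Day 526 onward. Vital-sign times from SAP Table 1 and footnote 7.

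**Step 1: assign each scheduled reading, with visits on their nominal days.**

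| Reading | Window it falls in | Distance from nominal day |
|---|---|---|
| Day 1, pre-dose | Baseline | – |
| Day 1, 4 h post-dose | Day 30 | abs(1 − 30) = 29 days |
| Day 90 | Day 90 | 0 |
| Day 270 | Day 270 | 0 |
| Day 450 | Day 450 | 0 |
| Day 540 | Day 540 | 0 |

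Only the 4-hour reading is misplaced, and it is the only scheduled reading in the Day 30 window.

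**Step 2: what could displace it.** A reading on day d replaces the 4-hour value if abs(d − 30) < 29.

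- Day 2: abs(2 − 30) = 28, replaces it.
- Day 58: abs(58 − 30) = 28, replaces it.
- Day 59: abs(59 − 30) = 29, a tie that the stated rule does not resolve.
- Day 60: abs(60 − 30) = 30, so the 4-hour value is kept.

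Any reading on Days 2 to 58 therefore displaces the 4-hour value. Such a reading would be unscheduled or come from an early end-of-study visit.

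**Step 3: a late reading that loses.** The Day 90 visit may be held up to 30 days early, and 90 − 30 = Day 60. Table 2 starts the Day 90 window on Day 61, so a visit on Day 60 falls in the Day 30 window. At 30 days from nominal against 29, it loses to the 4-hour value.

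**Step 4: number affected.** Planned randomisation is 750 + 750 = 1500. This is an upper bound, because it assumes that everyone is dosed, has the 4-hour reading, and has no closer reading on Days 2 to 58.

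**Step 5: repeat with the Day 30 window starting on Day 2 and a separate 4-hour time point.** The 4-hour reading goes to its own time point. No scheduled reading at its nominal day falls in Day 30. All other assignments are unchanged.

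**The case against.** The strongest reply is that the section specific to vital signs should govern. SAP 6.4.8.5 summarises by scheduled time point. The 4-hour reading is scheduled and Day 30 vital signs are not, so on that reading the plan already calls for a 4-hour summary and no Day 30 row. Table 2 is also organised by visit, and the 4-hour reading belongs to the Day 1 visit, which Table 1 labels baseline. It need not be treated as a separate later visit.

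This has force. A reader might infer that the 4-hour values will certainly be reported as a one-month effect, and the documents do not support that much: the mislabelling is what Table 2 produces, not the only possible outcome. The reply does not remove the conflict, though. Section 6.4.8.5 names no 4-hour time point and does not say that the windows are set aside. It also measures change from Day 1 when Day 1 has two vital-sign readings.

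Three further inferences should be resisted.

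- *That this is the trial's only acute post-dose measurement.* A 4-hour serum sample is also drawn on Day 1 for possible antibody testing, and footnote 4 of Table 1 allows extra vital signs or laboratory tests after later doses if needed. It is the only scheduled post-dose vital-sign reading.
- *That the comparison between arms is biased.* Both arms are windowed alike, so the comparison is mislabelled in time, not tilted toward either arm.
- *That a Day 30 row should simply be forbidden.* That would discard genuine unscheduled or early readings from Days 2 to 60, which 6.3.3 says are to be used.

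**Conclusion.** The point holds as an unreconciled conflict between SAP Table 2 and SAP 6.4.8.5. If Table 2 is applied to vital signs as written, the 4-hour systolic pressure, diastolic pressure and heart rate are tabulated 29 days from when they were taken, for up to about 1500 subjects.

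It is a minor point. It touches only the descriptive vital-signs tables by visit. SAP 6.3.3 keeps all data in the listings, so no value is lost. The categories of change to end of study in 6.4.8.5 use the pre-dose baseline and the final visit, and are unaffected. No efficacy endpoint moves, because lipids are not scheduled after dosing on Day 1 or at Day 30. It is still worth correcting: the cause is a stated window bound that gives the wrong label, not a detail left for later.

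The conclusion assumes that Table 2 applies to vital signs, which the SAP neither limits nor denies, and that visits fall on or near their nominal days.

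**What to change.** - **SAP Table 2:** start the Day 30 window on Day 2, and add a time point for vital signs at Day 1, 4 hours post-dose.
- **SAP 6.4.8.5:** summarise change from the pre-dose Day 1 value to 4 hours post-dose, by arm, as its own row. Name the pre-dose value as the reference for change.
- **Any Day 30 vital-signs row:** restrict it to readings taken on Days 2 to 60.

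The cost is one table row, one window bound and a sentence or two. No data collection changes and no scheduled lipid value moves. One side effect should be settled in the same edit: an as-needed laboratory value taken after dosing on Day 1 would no longer fall in any Table 2 window, so the SAP should say whether it still counts in the worst post-baseline laboratory summaries.

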6.3.4. Missing data handling

6.3.4.1 Efficacy

The sponsor will diligently follow up with each subject during the study through Day 540 \pm 14 days on all efficacy laboratory assessments of lipids/lipoproteins/biomarkers to keep missing data to a minimum regardless of whether the subject is on study treatment, uses ancillary therapies, experiences an adverse event, or adheres to the protocol (these data points are referred to as retrieved data). However, if missing data, defined as data not available from either scheduled (within the protocol defined visit window) or unscheduled visits, occurs for the primary or any of key secondary efficacy endpoints then that data will be imputed.

The primary method to impute missing data for the first co-primary efficacy endpoint (percentage change in LDL-C from baseline to Day 510) will be a multiple imputation washout model. The washout model will be performed on actual values, change and percentage change values are calculated after the imputation. All retrieved data for subjects who dropped out from study treatment are considered as non-missing data and will be utilized in all analyses. See [Appendix 2](#) for full details of the multiple imputation washout model.

In addition, sensitivity analyses using MMRM without multiple imputation and a control-based pattern mixture model (PMM, see details in [Appendix 3](#)) will be performed on the co-primary and key secondary efficacy endpoints to assess the impact of missing values. Note that the control-based PMM will be the primary method for imputing data for the second co-primary efficacy endpoint (time adjusted percentage change in LDL-C from baseline after Day 90 and up to Day 540).

Unless otherwise specified, missing data for all parameters not listed in the primary and key secondary endpoints will not be imputed and will be excluded from the associated analysis.

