#### 10.3.4. Missing Data Handling

Primary and key secondary efficacy endpoints will have missing data imputed using multiple imputation techniques (a primary method and sensitivity/exploratory methods). The primary imputation method will utilize a washout model for subjects in the inclisiran arm where it will be assumed that early terminating inclisiran sodium 300 mg subjects have missing data after their last observed assessment (monotone missing data) return to baseline values. The baseline values will be randomly sampled from a population estimated using baseline data from all subjects. One sensitivity technique includes control-based pattern mixture models which utilize placebo data for monotone missing inclisiran sodium 300 mg treatment data. Additional sensitivity data imputation techniques will be utilized. Retrieved data will be

utilized in all analyses where possible. Full details, including how intermittent missing data and missing placebo data will be handled, will be provided in the SAP.

Unless otherwise specified, other missing data will not be imputed.

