6.4.6.2. Secondary Efficacy Endpoints

The secondary efficacy endpoints will not be tested if either one of the co-primary efficacy endpoints' null hypothesis fails to be rejected.

The key secondary endpoints of this study are:

- Absolute change in LDL-C from baseline to Day 510.
- Time adjusted absolute change in LDL-C from baseline after Day 90 and up to Day 540.
- Percentage change from baseline to Day 510 in PCSK9, total cholesterol, ApoB, and non-HDL-C.

The Hochberg procedure [[Hochberg, 1988](#)] will be applied to control the family-wise type I error rate at a two-sided significance level of $\alpha=0.05$ for the key secondary endpoints.

Missing values will be imputed using the control-based PMM (see [Appendix 2](#) for more details) on LDL-C, PCSK9, total cholesterol, ApoB, and non-HDL-C, absolute change or percent change from baseline will be calculated based on imputed data before any analysis is performed.

The absolute change in LDL-C from baseline to Day 510 and percentage change from baseline to Day 510 in PCSK9, total cholesterol, ApoB, and non-HDL-C will be analyzed using a MMRM with covariates as specified in Appendix 1 and Appendix 3. Time adjusted absolute change in LDL-C from baseline after Day 90 and up to Day 540 will be analyzed similarly to that of time adjusted percentage change in LDL-C from baseline after Day 90 and up to Day 540.

MMRM without multiple imputation (see [Appendix 1](#)) will be used as sensitivity analyses for the key secondary endpoints.

The other secondary endpoints of this study are:

- Maximum percentage change in LDL-C. This is calculated by finding the smallest LDL-C value across all post baseline visits for each individual subject. This value will be used to compare with each subject's baseline value and calculate the percent change from baseline to the lowest LDL-C value.
- Absolute change from baseline to Day 510 in PCSK9, total cholesterol, ApoB and non-HDL-C.
- Absolute change and percentage change in LDL-C from baseline to each assessment time up to Day 540.
- Individual responsiveness defined as the number of subjects reaching on treatment LDL C levels of <25 mg/dL, <50 mg/dL, <70 mg/dL, and <100 mg/dL at Day 510.
- Proportion of subjects in each group with greater or equal to 50% LDL-C reduction from baseline.
- Absolute change and percentage change in other lipids, lipoproteins, apolipoproteins, and PCSK9 from baseline at each subsequent visit to Day 540.

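### The LDL-C responder endpoints default to observed cases, although secondary endpoints are assigned to ITT and Day 510 LDL-C is already imputed for the first co-primary endpoint

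*SAP*

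**What the plan says.** - **Scope of imputation.** In SAP 6.3.4.1, when missing data "occurs for the primary or any of key secondary efficacy endpoints then that data will be imputed". Gaps in any parameter outside those two groups of endpoints "will not be imputed and will be excluded from the associated analysis". Protocol 10.3.4 has the matching default: "Unless otherwise specified, other missing data will not be imputed".
- **Denominators.** SAP 6.3.1: "Percentages are based on the number of subjects in the analysis set for whom there are non-missing data, unless otherwise specified".
- **The endpoints.** SAP 6.4.6.2 lists two LDL-C responder endpoints as other secondary. One is "Individual responsiveness defined as the number of subjects reaching on treatment LDL"-C below four thresholds at Day 510. The other is "Proportion of subjects in each group with greater or equal to 50% LDL-C reduction from baseline", with no visit named. Binary endpoints get logistic regression with an odds ratio and 95% interval. No missing-data rule or pooling step is given for them, and p-values are nominal.
- **Population.** SAP 6.3.2.1: "The ITT population will be used for analysis of the primary and secondary endpoints". ITT is everyone randomized. SAP 6.3.2.3 defines mITT as dosed subjects with LDL-C at both baseline and Day 510, and SAP 6.4.6 makes mITT supportive.
- **Imputed LDL-C.** SAP Appendices 2 and 3 each produce 100 imputed datasets. SAP 6.3.4.1 says the washout model works on actual values, with changes calculated afterwards. Appendix 2 imputes missing inclisiran values from placebo, at Day 510 only. Appendix 3 (control-based pattern-mixture model, PMM) covers all visits.
- **Retrieved data.** SAP 6.3.4.1 counts samples taken after stopping treatment as non-missing in every analysis.

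**The concern.** One measurement, Day 510 LDL-C, is treated in two ways. In the first co-primary analysis, an inclisiran subject without a Day 510 value stays in and receives a placebo-like one. In the responder analysis of the same value, that subject leaves both numerator and denominator.

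Two consequences follow. First, an analysis labelled ITT would run on nearly the mITT set, so the mITT result would add little as support. Second, the reported proportions and odds ratios would rest on a more favourable assumption about missing inclisiran subjects than the primary result does. Attainment of prespecified LDL-C targets is a named secondary objective (SAP 2.2), so the mismatch affects a result that the trial means to report.

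**Working it through.** **Step 1. The plan's own figure.** SAP 6.1 gives about 5% drop-out and about 1425 evaluable subjects: 1500 × (1 − 0.05) = 1425. This reproduces. If missing Day 510 values matched that drop-out, an observed-case analysis would use about 1425 of 1500 ITT subjects and omit about 75.

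**Step 2. Which rule applies.** Nothing in SAP 6.4.6.2 or the appendices specifies imputation for the responder endpoints. The defaults in SAP 6.3.4.1, Protocol 10.3.4 and SAP 6.3.1 all point to observed cases.

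**Step 3. Formula.** Let m be the share missing in the inclisiran arm, p the observed inclisiran response rate and q the placebo rate. If missing inclisiran subjects respond like placebo:

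- all-randomized inclisiran rate = (1 − m) × p + m × q
- excess of the observed-case rate = m × (p − q)

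Two simplifications apply. The imputation conditions on baseline LDL-C and lipid-therapy use, whereas q here is one average rate. The placebo rate is taken as unchanged, because placebo gaps are imputed as missing at random.

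**Step 4. Numbers at m = 5%.** The documents give no response rates, so every p and q is an assumption. The only anchor is the Phase II mean LDL-C reduction of around 50% (Protocol 1.2.2.2), which makes a rate near one half plausible for the 50% endpoint.

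| Assumed p vs q | Excess = 0.05 × (p − q) | Inclisiran rate after |
|---|---|---|
| 20% vs 0% | 1.0 points | 19.0% |
| 40% vs 2% | 1.9 points | 38.1% |
| 90% vs 50% | 2.0 points | 88.0% |
| 50% vs 2% | 2.4 points | 47.6% |
| 80% vs 30% | 2.5 points | 77.5% |
| 70% vs 2% | 3.4 points | 66.6% |
| 85% vs 10% | 3.75 points | 81.25% |

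The range is about 1 to 4 points.

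**Step 5. Sensitivity to m.** The excess is proportional to m. Over the same rows it is 0.4 to 1.5 points at m = 2% (0.02 × 20 and 0.02 × 75) and 2.0 to 7.5 points at m = 10% (0.10 × 20 and 0.10 × 75). If missing subjects respond like observed subjects in their own arm, it is 0.

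**Step 6. Treatment comparison.** For 50% vs 2% at m = 5%, the difference falls from 48.0 to 47.6 − 2 = 45.6 points. The odds ratio falls from (0.50/0.50)/(0.02/0.98) = 49.0 to (0.476/0.524)/(0.02/0.98) = 44.5. Power of a two-proportion comparison rounds to 1.000 before and after the change for the 40% vs 2%, 50% vs 2%, 70% vs 2% and 80% vs 30% rows, at m = 2%, 5% and 10%.

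**The case against.** - **The rule may not reach LDL-C.** It speaks of *parameters* not listed in the primary and key secondary endpoints, and LDL-C is a listed parameter. This reading is possible, but the Protocol default and the denominator rule point the other way. It also leaves a gap: the SAP would not say which imputed datasets to use or how to pool the logistic results.
- **Overstatement is not established.** A reader might infer that the response rates will be overstated. The documents support only a conditional statement. The excess follows under the placebo-like assumption and vanishes if missing subjects resemble observed ones. The SAP itself uses missing-at-random assumptions for placebo and in its sensitivity MMRM. This stands.
- **The set is not completers.** A reader might infer a completer analysis. SAP 6.4.1 defines completers by the Day 540 visit, whereas observed cases include treatment discontinuers with a Day 510 sample. Protocol 4.4.1 asks for follow-up through Day 540 after discontinuation, and the analysis window of Days 481 to 525 accepts unscheduled samples. Missing Day 510 data could therefore be below 5%. This stands and reduces the size.
- **The 50% endpoint may not concern Day 510.** If it means any visit, a missing Day 510 value need not remove a subject, and the washout datasets would not suffice for inclisiran. This stands; the point covers that endpoint only if Day 510 is meant.
- **On-treatment wording.** The target endpoint counts subjects reaching on-treatment levels, and filling gaps with placebo-like values may change that quantity. The objection is fair, but the wording already sits awkwardly beside the retrieved-data rule and needs clarification in any case.
- **Washout is not compelled.** Absolute change in LDL-C at Day 510 uses the control-based PMM. Either set could serve; washout has the merit of matching the first co-primary.

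**Conclusion.** The point holds in a limited form. On the natural reading, the Day 510 target endpoints, and the 50% endpoint if it refers to Day 510, are observed-case analyses in a set close to mITT. This does not fit the assignment of secondary endpoints to ITT or the imputation of the same value for the first co-primary.

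Under the SAP's placebo-like assumption, the inclisiran rate would be about 1 to 4 percentage points too high at 5% missing. That range rests on assumed response rates and on equating drop-out with missing Day 510 data.

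A reader might also infer that a claim of efficacy is at risk. It is not: these endpoints lie outside the Hochberg family and carry nominal p-values. What would change is the reported proportions and odds ratios and their consistency with the primary analysis. The change is worth making because it is cheap and removes a contradiction within the plan.

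**What to change.** Amend SAP 6.3.4.1 and 6.4.6.2 as follows:

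1. Derive Day 510 responder status in ITT from the 100 washout-imputed LDL-C datasets. Thresholds can be applied directly, because imputation is on actual values.
2. Fit the planned logistic model in each dataset, pool log odds ratios by Rubin's method, and report proportions averaged over datasets. Where placebo responders are near zero, as may happen for <25 mg/dL, the log odds ratio can be unstable; pool risk differences instead.
3. Keep the observed-case result as a sensitivity analysis.
4. Name the visit for the 50% endpoint. If it is not Day 510, use the Appendix 3 datasets, which cover all visits for inclisiran.
5. State what on treatment means for the target endpoint, and reconcile it with the rule that retrieved data count as non-missing.

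The cost is a small programming effort on datasets that the plan already creates, and response rates that may come out slightly less favourable.
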